12.7 Follow-up Procedures for Adverse Events

The investigator may be asked to provide follow-up information to the GW PVD for any AEs reported or during the investigation of potential safety issues. Such requests for additional safety information may occur post Visit 11, after the trial.

Adverse events considered related to the IMP by the investigator or the sponsor should be followed up until resolution or the event is considered stable.

It will be left to the investigator's clinical judgment whether or not an AE is of sufficient severity to require the patient's removal from treatment. A patient may also voluntarily discontinue from treatment due to what is perceived as an intolerable AE. Further details of discontinuation are presented in [Section 10](#). If either of these occurs, the patient must permanently discontinue from treatment and be given appropriate care under medical supervision until symptoms cease or the condition becomes stable. If a safety concern is identified following withdrawal of a patient, GW may contact the investigator for additional follow-up information.

12.8 Potential Cases of Drug-induced Liver Injury

All investigational sites are required to submit to the GW PVD the laboratory results for any patient after randomization that meets the criteria for the selected laboratory parameters as follows:

- ALT or AST $> 3 \times$ ULN with the appearance of fatigue, nausea, vomiting, right upper quadrant pain or tenderness, fever, rash, and/or eosinophilia ($> 5\%$).
- ALT or AST $> 8 \times$ ULN.

Study Code: GWND18064

EudraCT Number: 2018-003370-27

Clinical Protocol 4.1, 07Jul2020 (duplicate synopsis removed)

- ALT or AST $> 5 \times$ ULN for more than 2 weeks.
- ALT or AST $> 3 \times$ ULN **and** (TBL $> 2 \times$ ULN **or** INR > 1.5).

These reports must be sent to the GW PVD via e-mail (see **APPENDIX 2**) within 24 hours of becoming aware of the results. In addition, please send a copy of the patient's baseline laboratory results with all reports to the GW PVD.

Abnormal values in AST and/or ALT concurrent with abnormal elevations in TBL that meet the criteria outlined above are considered potential cases of drug-induced liver injury and will be considered as protocol-defined criteria for treatment discontinuation and important medical events. The investigator will arrange for the patient to return to the investigational site as soon as possible (within 24-48 hours of notice of abnormal results) for repeat assessment of ALT, AST, TBL, INR, % eosinophils, alkaline phosphatase and gamma-glutamyl transferase levels, detailed history and physical examination. Patients should be followed in this way until all abnormalities have normalized (in the investigator's opinion) or returned to the baseline state. However, if the above transaminase elevation criteria are confirmed by the first set of follow-up laboratory tests, the patient must permanently discontinue the IMP.

Elevations in ALT or AST $> 3 \times$ ULN **or** TBL $> 2 \times$ ULN alone are not considered potential cases of drug-induced liver injury, but will be followed as detailed above, within 72 hours' notice of abnormal results. If the patient cannot return to the investigational site, repeat assessments may be done at a local laboratory and the results sent to GW PVD.

12.9 Notification of Safety Information to Investigators, Regulatory Authorities and IRBs/IECs.

In accordance with the EU Clinical Trials Directive, relevant parts of the FDA Code of Federal Regulations and any national regulations, GW will inform investigators, regulatory authorities and relevant IRBs/IECs of all relevant safety information. This will include the reporting of relevant SAEs and all suspected unexpected serious adverse reactions (SUSARs).

This information will be provided through 2 sources:

1. IB⁶⁴: a compilation of the clinical and non-clinical safety data available on the IMP that is relevant to the trial. The IB is updated at least annually or when important new safety information becomes available.

Study Code: GWND18064

EudraCT Number: 2018-003370-27

Clinical Protocol 4.1, 07Jul2020 (duplicate synopsis removed)

2. Council for International Organizations of Medical Sciences (CIOMS) reports: these reports are issued every time a SUSAR is reported to GW. They provide information on individual case reports and are sent to all the regulatory authorities, the relevant central ECs which have approved the trial and investigators. As required, the investigator should notify their regional IRBs/IECs of SAEs or SUSARs occurring at their site and other AE reports, i.e., CIOMS reports and any additional safety documentation received from GW, in accordance with local procedures.

In the US, investigators are normally required to report promptly to their IRBs all unanticipated problems involving risks to patients, or others, including AEs that should be considered unanticipated problems. Based on current FDA guidance the following clarification is provided in determining what constitutes an unanticipated problem:

In general, an AE observed during the conduct of a trial should be considered an unanticipated problem involving risk to patients and reported to the IRB, *only* if it were unexpected, serious, and would have implications for the conduct of the trial (e.g., requiring a significant, and usually safety-related, change in the protocol such as revising inclusion/exclusion criteria or including a new monitoring requirement, informed consent/assent, or IB). An individual AE occurrence *ordinarily* does not meet these criteria because, as an isolated event, its implications for the trial cannot be understood.

The FDA guidance states that, accordingly, to satisfy the investigator's obligation to notify the IRB of unanticipated problems, any investigators participating in a multisite trial may rely on the sponsor's assessment and provide to the IRB a report of the unanticipated problem prepared by the sponsor.

GW will inform investigators, regulatory authorities and relevant IRBs/IECs of any safety issues or case reports that are considered to be unanticipated and provide such reports as mentioned above. It should be noted that a single SUSAR report notified to investigators in the trial does not necessarily constitute an unanticipated problem unless identified by GW in the submission cover letter.

As a minimum, the recipient will be sent all of the above and relevant updates between the period from ethical approval and final database lock.

Study Code: GWND18064

EudraCT Number: 2018-003370-27

Clinical Protocol 4.1, 07Jul2020 (duplicate synopsis removed)

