8.2 Concomitant Therapy

It is theoretically possible that GWP42003-P may modify the metabolism of other drugs (including AEDs) administered concurrently and there remains the possibility of pharmacological interactions between GWP42003-P and other concurrently administered drugs. Doses of any concomitant medications for RTT-related symptoms (including AEDs) must have been stable for at least 4 weeks prior to screening and should be expected to remain stable throughout the trial period. If there are side-effects suspected of being related to an elevation in the concomitant concentration, the investigator should contact the GW medical monitor to discuss best management. Decisions should be based on clinical symptoms and not plasma levels of concomitant medications. The final decision regarding dose adjustments should be taken by the investigator. CBD has the potential to induce the expression of hepatic cytochrome P450 (CYP450) enzymes (CYP1A2, 2B6 and 3A4) at clinically relevant concentrations. Careful titration of CBD in patients taking concomitant medications metabolized by CYP3A4, CYP2C19 or CYP2B6 is advised, with plasma monitoring of such medications or their metabolites to be undertaken at the investigator's discretion. Further information on drug interactions can be found in the IB⁶⁴. Concomitant medication dose reductions are permitted on clinical grounds (e.g., due to AEs or transaminase elevations not meeting IMP discontinuation

Study Code: GWND18064

EudraCT Number: 2018-003370-27

Clinical Protocol 4.1, 07Jul2020 (duplicate synopsis removed)

criteria specified in [Section 10](#) and [Section 12.8](#)). Dose adjustments should be discussed with the GW medical monitor. Any concerns regarding potential interactions with concomitant medications can be discussed with the trial medical monitor(s).

Any non-pharmacological interventions (e.g., physical therapy, speech therapy, dietary supplements, probiotics etc.) must also be stable for 4 weeks prior to screening and the patient/caregiver must be willing to maintain a stable regimen throughout the trial.

The use of rescue medication is allowed when necessary (i.e., AED for transient exacerbation of seizures). Any medication, other than the IMP, taken during the trial must be recorded on the electronic case report form (eCRF).

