Aspartate aminotransferase	Mean corpuscular hemoglobin	pH		
Calcium	Platelets	Protein		
Creatine kinase	Red blood cell count	White blood cells		
Creatinine	White blood cell count with automated differential	Bilirubin		
Creatinine clearance		Ketones		
Gamma-glutamyl transferase		Specific gravity		
Glucose		Urobilinogen		
Human chorionic gonadotropin				
HDL-cholesterol				
IGF-1*				
Potassium				
Prolactin				
Prothrombin time (plasma)				
Sodium				
Total bilirubin				
Total protein				
Triglycerides				
Urea (blood urea nitrogen)				

*Visits 1 and 9 only; IGF-1 laboratory results to remain blinded throughout the trial.

¹Dipstick at site or analysed at a central laboratory.²Analysed at the trial site by use of a dipstick (if allowed per local regulations).

HDL = high density lipoprotein

Investigators at trial sites will be notified of laboratory test results. All laboratory results will be reviewed, and the reports signed and dated by an investigator. Any results considered to be of clinical significance must be addressed and followed up as clinically appropriate. The results of THC screening will be reported back to the study site to permit confirmation of eligibility. All laboratory results considered to represent an AE must be documented on the eCRF. For reporting and follow-up of potential cases of drug-induced liver injury, see [Section 12.8](#).

Study Code: GWND18064

EudraCT Number: 2018-003370-27

Clinical Protocol 4.1, 07Jul2020 (duplicate synopsis removed)

Repeat samples will be taken, if required, for clinical follow-up or if the sample is lost or damaged. Any abnormal end of treatment clinical laboratory result of clinical significance must be repeated at regular intervals until it returns to normal, or until an investigator is satisfied that the abnormality is not related to the IMP and needs no further investigation. Blood sample volume requirements and processing procedures will be detailed in a separate laboratory manual; the maximum cumulative amount of blood taken in any 4-week period, including PK blood samples, will be 2.55 mL/kg of body weight and will not exceed a total of 50 mL within any 8 week period⁶⁷, taking into account possible repeat tests. The patient/caregiver must be advised that it may not be safe for the patient to undertake further blood tests within 1 month of any trial-related blood draws and to inform the investigator if they suffered any blood loss during the 1-month period leading up to a planned blood draw.

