10 IMP DISCONTINUATION AND WITHDRAWAL

In accordance with the Declaration of Helsinki, the International Council for Harmonisation (ICH) Harmonised Guideline: Integrated Addendum to ICH E6(R1): Guideline for Good Clinical Practice (GCP) E6(R2), the FDA regulations relating to GCP and clinical trials, the EU Clinical Trials Directive, the EU GCP Directive and/or other applicable regulations, a patient has the right to withdraw from the trial at any time and for any reason, with no obligation to provide a reason, and without prejudice to his or her future medical care by the physician or at the institution.

The patient must be permanently discontinued from treatment if any of the following apply:

- Administrative decision by the investigator, GW, or a regulatory authority.
- Pregnancy.
- Protocol deviation that is considered to potentially compromise the safety of the patient.
- Withdrawal of patient assent.
- Withdrawal of parent(s)/legal representative consent.
- ALT or AST $> 3 \times$ ULN with the appearance of fatigue, nausea, vomiting, right upper quadrant pain or tenderness, fever, rash, and/or eosinophilia ($> 5\%$).
- ALT or AST $> 8 \times$ ULN.
- ALT or AST $> 5 \times$ ULN for more than 2 weeks.
- ALT or AST $> 3 \times$ ULN **and** (TBL $> 2 \times$ ULN **or** INR > 1.5).

Note: Prior to treatment discontinuation for the transaminase elevations noted above, the investigator may choose to confirm the transaminase elevations by repeating the following laboratory tests within 24–48 hours: ALT, AST, TBL, INR, % eosinophils, gamma-glutamyl transferase and alkaline phosphatase.

Should the above transaminase elevation criteria be confirmed, the patient must permanently discontinue the IMP. In cases where transaminase elevation IMP discontinuation criteria are not met or confirmed, the dose of IMP or a concomitant medication with known hepatotoxicity may be reduced. Dose adjustments should be discussed with the GW medical

Study Code: GWND18064

EudraCT Number: 2018-003370-27

Clinical Protocol 4.1, 07Jul2020 (duplicate synopsis removed)

monitor. The final decision regarding dose adjustments should be taken by the investigator.

- Lost to follow-up.

The patient may also be permanently discontinued from treatment for any of the following:

- Patient or caregiver non-compliance.

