12.2 Serious Adverse Events

During clinical investigations, AEs may occur which, if suspected to be IMP-related, might be significant enough to lead to important changes in the way the IMP is developed (e.g., change in dose, population, monitoring need, consent/assent forms). This is particularly true for events that threaten life or function. Such SAEs will be reported promptly to regulatory authorities, applicable IRBs/IECs and investigators (expedited reporting) by GW.

An AE must only be classed as serious, i.e., a SAE, when the event falls into 1 of the following criteria:

- Results in death.
- Is life-threatening*.

Study Code: GWND18064

EudraCT Number: 2018-003370-27

Clinical Protocol 4.1, 07Jul2020 (duplicate synopsis removed)

- Requires inpatient hospitalization or prolongation of existing hospitalization.
- Results in persistent or significant disability/incapacity.
- Is a congenital anomaly/birth defect.
- Is medically significant^{**}.

^{*} The term “life-threatening” in the definition of “serious” refers to an event in which the patient was at risk of death at the time of the event; it does not refer to an event which, hypothetically, might have caused death if it were more severe.

^{**} Medical and scientific judgment should be exercised in deciding whether SAE reporting is appropriate in other situations. Important medical events may not be immediately life-threatening or result in death or hospitalization but may jeopardize the patient or may require intervention to prevent one of the other outcomes listed in the definition above. These should also usually be considered serious. Examples of such events are intensive treatment in an emergency room or at home for allergic bronchospasm, blood dyscrasias or convulsions that do not result in hospitalization, or development of drug dependency or use of drugs of abuse.

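### Protocol Section 12.8: the 72-hour rule for transaminase rises 'alone' contradicts the section's own list of liver criteria (minor)

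*Protocol*

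**What the plan says.** **Section 12.8, list.** Four criteria are given:
- ALT or AST above 3 x ULN with symptoms or eosinophilia;
- above 8 x ULN;
- above 5 x ULN for more than 2 weeks;
- above 3 x ULN with TBL above 2 x ULN or INR above 1.5.

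Results meeting any of them go to the sponsor's pharmacovigilance department "within 24 hours of becoming aware of the results".

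**Section 12.8, label and recall paragraph.** "Abnormal values in AST and/or ALT concurrent with abnormal elevations in TBL that meet the criteria outlined above are considered potential cases", meaning liver injury caused by the drug. The same sentence makes them discontinuation criteria and important medical events. The investigator must then bring the patient back within 24-48 h for a repeat liver panel, "detailed history and physical examination". The paragraph ends by requiring permanent discontinuation if the transaminase criteria set out above are confirmed at the first follow-up tests.

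**Section 12.8, last paragraph.** ALT or AST above 3 x ULN, or TBL above 2 x ULN, "alone are not considered potential cases of drug-induced liver injury, but will be followed as detailed above, within 72 hours' notice of abnormal results".

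**Other sections.**
- Section 10 makes the same four criteria mandatory stops. Before stopping, the "investigator may choose to confirm the transaminase elevations by repeating the following laboratory tests within 24–48 hours".
- Section 9.2.10 points to Section 12.8: "For reporting and follow-up of potential cases of drug-induced liver injury".
- Section 8.2 allows concomitant-drug reductions "due to AEs or transaminase elevations not meeting IMP discontinuation" criteria, and names both Section 10 and Section 12.8 as the place where those criteria are found.
- Section 12.2 says of seriousness: "Medical and scientific judgment should be exercised in deciding whether SAE reporting is appropriate in other situations".

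**The concern.** A result that meets a listed liver criterion should lead to one instruction. Here an isolated ALT of, say, 9 x ULN is a listed criterion under a heading about potential DILI and a mandatory stop under Section 10. By the last paragraph of the same section it is also not a potential case and need only be followed within 72 h. Section 9.2.10 sends sites to Section 12.8 for follow-up, so they would apply its wording.

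Three things are at stake: how soon the patient is seen for repeat tests, history and examination; whether the event carries the potential-DILI label; and whether the investigator is prompted to treat it as an important medical event. Two features of the trial give this some weight. Section 3.2.2 reports transaminase rises with this drug and no accompanying bilirubin above 2 x ULN, so a label tied to bilirubin leaves out the pattern already seen. It gives no magnitudes, so whether any past case reached either criterion is unknown. Patients are also profoundly cognitively impaired (Section 9.2.17.9), so symptoms such as nausea or abdominal pain may be hard to elicit and a prompt examination is worth more. Against this, Section 3.3.3 expects a lower transaminase risk here than in the earlier programme.

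**Working it through.** The plan states no figure to reproduce. The check applies the rules of Sections 10 and 12.8 to each way of meeting the list. The last criterion has two arms, so there are five routes.

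| Route | Mandatory stop (10) | 24 h report (12.8) | Label and important-medical-event status (12.8) | Recall limit from the label sentence and the 'alone' rule |
|---|---|---|---|---|
| (a) >3 x ULN with symptoms or eosinophilia, TBL normal | yes | yes | not stated | not stated |
| (b) >8 x ULN, isolated | yes | yes | no | 72 h |
| (c) >5 x ULN for more than 2 weeks, isolated | yes | yes | no | 72 h |
| (d) >3 x ULN with TBL >2 x ULN | yes | yes | yes | 24-48 h |
| (e) >3 x ULN with INR >1.5, TBL normal | yes | yes | not stated | not stated |

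**Step 1: the literal reading.** Routes (b) and (c) are both above 3 x ULN. The last paragraph sets ALT/AST against TBL, so 'alone' can be read as one raised without the other. It gives no upper bound and no exception for listed criteria. On that reading 2 of 5 routes are 72 h non-cases.

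**Step 2: the sentence that points the other way.** The recall paragraph closes by referring back to the transaminase criteria above. Section 10 uses the same phrase for its full list of four, and in Section 12.8 that list also stands above. Read this way, the 24-48 h visit is where any of the four criteria is confirmed, and it covers all five routes, including (a) and (e). The 'alone' sentence then contradicts it for (b) and (c).

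**Step 3: does Section 10 fill the gap?** It settles stopping. Its 24-48 h repeat is optional, covers laboratory tests only and serves confirmation before stopping. For an investigator who stops at once, Section 12.8 is the only section that sets a time for seeing the patient.

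**Step 4: size of the timing difference.**
- Outer limit: 72 - 48 = 24 h later; 72 / 48 = 1.5 times.
- Route (c): more than 14 x 24 = 336 h have already passed, and 24 / 336 = 0.071, so the difference is at most about 7% of the time elapsed. The first value above 5 x ULN was already above 3 x ULN, so the patient should already be under follow-up.
- Route (b): this is where the 24 h can matter.

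**Step 5: what does not change.** Stopping and the 24 h report cover 5 of 5 routes. The 72 h follow-up refers back to the same procedures, so its content is the same. SAP Section 9.2.1 counts ALT and AST above 3, 5 and 8 x ULN whatever the label, so the liver table is unaffected.

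**The case against.** The best defence is that the intended meaning is clear enough. The thresholds in the 'alone' sentence, ALT/AST above 3 x ULN and TBL above 2 x ULN, are the two parts of the combined criterion, so 'alone' naturally means without whatever would make it a listed criterion. The entries for 8 x ULN and for 5 x ULN over 2 weeks are specific, and a general rule should not override them. The recall paragraph's closing sentence, the section heading and the cross-reference in Section 8.2 all suggest that four criteria count. If the bilirubin link was deliberate for the label, it fits Section 3.2.2, which judges severe injury by Hy's Law. General provisions also apply: clinically appropriate follow-up of significant results (9.2.10), unscheduled safety visits (9.1.3) and medical supervision after removal from treatment (12.7).

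Most of this stands, and it caps the size of the point. It does not remove the conflict, because the last paragraph makes no exception and the general provisions set no time. A site that reads the last paragraph literally gets a different limit from one that reads the recall paragraph.

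A reader might infer something stronger: that a patient above 8 x ULN could stay on full dose for 72 h, go unreported, or have no defined follow-up. The documents do not support this. Section 10 requires either stopping or confirmation within 24-48 h, so no extra doses follow. The 24 h report covers all four criteria, and the 72 h follow-up has the same content. Nor can it be said that routes (a) and (e) have no recall window at all, since the recall paragraph's closing sentence reaches them.

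**Conclusion.** Section 12.8 is internally inconsistent, and the point is minor. For isolated ALT/AST above 8 x ULN, and above 5 x ULN for more than 2 weeks, the literal text moves the outer recall limit from 48 h to 72 h and withholds the potential-DILI label and the important-medical-event prompt. The time matters mainly for the first route; for the second the loss is chiefly the label. The loss of the prompt is itself limited, because Section 12.2 leaves seriousness to medical judgment.

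This rests on reading 'alone' as a transaminase rise without raised TBL, which the wording allows but other text in the section argues against. The route counts describe the text, not patients: the documents give no frequency for either route, so the number of patients affected cannot be estimated.

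**What to change.** In the last paragraph of Section 12.8, change 'alone' to 'alone, and not meeting any criterion listed above'. In the recall paragraph, state that the 24-48 h return, with its repeat panel, history and examination, applies to all four listed criteria. Extending important-medical-event status to all four is optional.

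The cost is a wording amendment to one section, a note to sites and a few earlier recalls. If event status is also extended, more events may be handled as important medical events. No scheduled visits, samples or patients are added, and the SAP needs no change. The remaining benefit is limited, because SAP Sections 1 and 9.5 record the sponsor's decision to discontinue the trial.
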